- b. Withdrawal/Termination criteria: Participants are free to abstain from taking their statins and leave the study at any time. We will test both muscle enzymes (creatine kinase) and liver enzymes (ALT) to determine if statins are causing either muscle myopathies or liver injury. This testing will occur at baseline and at 1 month into taking

statins. If enzymes are elevated, the subject will be taken out of the study for their own health.

E. Specific methods and techniques

This study will require approximately 13 total testing visits. The total time commitment of study visits is approximately 30 hours over the 12 months of participation.

a. Testing Procedure

- i. Telephone screen: A telephone screen will be used to collect health history, concurrent medications, and physical activity level of potential participants prior to in-person screening.
- ii. Blood draw: A screening blood draw will be used to determine presence of genetic markers associated with increased risk of myopathy from statin, creatine kinase (CK), kidney function (GFR) and liver enzymes (ALT). CK, GFR and ALT will be used to detect abnormal muscle, kidney or liver function prior to enrollment. A blood draw will be repeated at 1 month to measure for myopathy, and changes in

liver and kidney function from statin use. The study physician will be allowed to request additional lab tests to ensure participant's safety. In some cases, when the participant is not close to any milestone, that will mean an additional visit to obtain the blood draw.

- iii. Brief Pain questionnaire: this survey will be used at screening, month 1, 6, and 12 to subjectively assess general pain in participants. This measure will be used to measure if pain levels have changes during the intervention. It will specifically be useful in participants who decide to withdraw.

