i. Exercise: Some risks are associated with the exercise testing used to assess maximal aerobic capacity. Cardiovascular events during maximal exercise and in recovery are possible but rare in this population (1). However, these risks could be serious. Therefore, initial screening by maximal stress test will be performed in a clinical setting under the direction of a medical monitor (medical monitor only supervises the graded exercise test). Muscle soreness and strain are possible with exercise testing, but these are not a serious risk. The maximal aerobic capacity test represents greater risk of cardiovascular events than the training exercise because of the increased intensity of the exercise. However, events are extremely

- rare, and participants will be screened for risk of cardiovascular disease and symptoms. Emergency equipment, including defibrillator, and ambulance plan are available for all participants.

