- ii. Statins: Statin therapy is associated with muscle issues that range from more minor issues of muscle pain, cramping and fatigue, to myopathies, to the very severe issues of rhabdomyalgia, although this is rare. Statins are the most prescribed drug in the world. Statins are also associated with headaches, nausea, and constipation. Statins are also not well tolerated by athletes suggesting that exercise may worsen the effects of statins on skeletal muscle. Thus, there is the potential that participants in our study may have adverse effects while taking statins. A recent trial conducted by our consultant, [name], utilized 80 mg/day of atorvastatin and found that ~15% of participants experienced pain and weakness (2). atorvastatin 80 mg is an increasingly common dose because three large clinical trials, REVERSAL (atorva 80 v. prava 40, n=502) (3), PROVE IT (atorva 80 v. prava 40, n=4,162) (4), and TNT (atorva 80 v. prava 10, n=10,001) (5) demonstrated reduced atherosclerosis and cardiac events with atorvastatin 80 mg. These studies were done in CAD patients, a group on multiple other medications and likely to be at higher risk for side effects than our healthy participants. Nevertheless, side effects were rare. Liver function test (>3 times upper normal limits [UNL]) and creatinine kinase (CK) elevations (> 10 UNL) occurred in only 1-3.3% of patients treated with atorvastatin 80 mg for up to 24 months, respectively. These side effects should be even more rare given that we will pre-screen and exclude individuals with polymorphisms (GATM and SLC01B1) that increase risk for myopathy. We will test both muscle enzymes (creatine kinase) and liver enzymes (ALT) to determine if statins are causing either muscle myopathies or liver injury. This testing will occur at baseline and at 1 month into taking statins. If enzymes are elevated, the subject will be taken out of the study for their own health. Finally, study physicians at both KUMC who commonly prescribe statins and deal with patients who experience statin induced problems will provide medical coverage for our studies. Participants are free to abstain from taking their statins and leave the study at any time. Importantly, most individuals report that statin induced complications go away very quickly after stopping the therapy. Participants who are discontinued from the study for a medical reason judged to be appropriate by the study doctors will receive the same reimbursement as if they completed the study to avoid the possibility that a subject would "soldier on" simply for the reimbursement.

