- a. Participants will be recruited from the KUMC campus, from hospitals and clinics associated with KUMC and metro-Kansas City, Kansas and Missouri areas. Study team will also use BPA system through Epic to recruit participants. Recruiting will occur through physicians and clinics and through advertisements in emails, flyers, newspaper ads, radio spots, etc. Interested participants will call or email and undergo initial phone screening, conducted by trained study staff, to see if they qualify. Should they meet the initial qualifications, they will come to the lab for an informed consent meeting with the PI, research coordinator, or other study staff. They will then be provided with an informed consent that is fully approved by the IRB at KUMC to review prior to the inperson meeting. Participants who are interested in taking part in the study will be asked to sign the informed consent in the presence of a witness. Participants will have adequate opportunity to review the informed consent and to ask any questions they may have about the research protocol, compensation, risks, and benefits of taking part in the study.
- **b.** The targeted/ planned distribution of participants by sex/gender and racial/ethnic groups for the proposed study or protocol will follow the local demographics. The Kansas City area has a population that is comprised of 13 % African American, 2% Asian, 5% Hispanic, and 80% Caucasian. It is anticipated that the study population at KUMC will have much the same racial and ethnic make-up. Statistical comparisons among minorities or between minority and Caucasian groups are not aims of the current study. We fully intend to enroll every eligible minority individual in these studies. Ample pools of all targeted populations exist.

- **c.** Selection criteria: It is anticipated that women will comprise approximately 50% of the study participants. It is also anticipated that gender will not be a significant factor in the response to exercise training or statin therapy, and hence, it is anticipated that the data from both genders will be compiled and analyzed as a group.
- **d.** Exclusions: No minority groups will be excluded.
- **e.** Outreach: The subject pool will be limited to the greater Kansas City (MO and KS) area. Subject will need to make regular visits to the laboratories, and thus, participants will only be recruited who are within the county region and can regularly make appointments.
- B. Screening Interview/questionnaire: NA

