- C. Informed consent process and timing of obtaining of consent: Should the participant meet the initial qualifications, they will come to the lab for an informed consent meeting with the PI, research coordinator, or other study staff. They will be provided with an informed consent that is fully approved by the IRB at KUMC to review prior to the in-person meeting. Participants who are interested in taking part in the study will be asked to sign the informed consent in the presence of a witness. Participants will have adequate opportunity to review the informed consent and to ask any questions they may have about the research protocol, compensation, risks, and benefits of taking part in the study.
- **D. Alternatives to Participation:** NA
- **E.** Costs to Participants: There is no cost to participants for participation in this study.
- **F.** How new information will be conveyed to the study subject and how it will be documented: New information about risks associated with involvement in the study will be disseminated but no other information will be disclosed.
- **G. Payment, including a prorated plan for payment:** Participants will receive a one-time compensation of \$600 for completing all study visits. If participation ends early, participants will receive \$75 for each study visit excluding screening. They will be given a ClinCard, which works like a debit card. After completion of the study, payment will be added to the card by computer. The money will be available within 1 business day. Participants can use the ClinCard at an ATM or at a store. Study staff will collect their name, address, and social security number to allow them to set the participant up in the ClinCard system through the KUMC Research Institute. Study payments are taxable income. A form 1099 will be sent to the subject and the Internal Revenue Service if your payments are \$600 or more in a calendar year. The participants' personal information will be kept on a secure computer. It will be removed from the computer after the study is over and the money on the card has been used. The information will not be shared with other businesses. It will be kept confidential.
- **H. Payment for a research-related injury:** We will include the following text in the consent form: "All forms of medical findings, whether routine or experimental, involve some risk of

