- A. Statistical and Data Analysis: This project is a two-factor study. One factor is treatment group (between participants) and a second factor is time of data collection (0, 1, 6, and 12 months) (within subject). The data analysis will be carried out for the primary outcome variable of mitochondrial respiration in addition to other outcome variables (VO₂peak and insulin sensitivity, etc.). For each measure, its baseline measure and age will be added as covariates to adjust for the individual difference at baseline. Two-way interaction between treatment and time will be added in the model for testing if the outcome changes differently between groups over time. Additional variables, such as demographics, BMI, physical activity, etc. may also be included as covariates. If the test of trend difference is significant, then the comparison at each time point will also be considered to identify when the difference between groups reaches the maximum. Least Square Means will be used for the aforementioned comparisons. The statistical analysis will be performed with mixed procedure in STATA 13.1 (StataCorp LP, College Station, TX). Mixed model does not require complete data for a longitudinal study. Residual analyses will be conducted and efforts to address those will be made, including appropriate transformations.

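### Does the payment rule in section III.G reward a participant for leaving before the last visit?

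*Combined protocol and SAP*

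**What the plan says.** Section III.G gives two amounts: a one-time sum in dollars of "600 for completing all study visits. If participation ends early, participants will receive" a rate of "75 for each study visit excluding screening". It sets no ceiling on the second amount and does not say how many visits earn it.

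Other sections bear on the count without settling it:

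- Section II.E: "This study will require approximately 13 total testing visits". The total is approximate and is not divided into screening and later visits.
- Section II.E.a.ii: "A screening blood draw will be used to determine presence of genetic markers". The same item lets the study physician order further laboratory tests, which may need an extra visit.
- Section II.F.a.i: "initial screening by maximal stress test will be performed in a clinical setting".
- Section III.A.a, on people who pass the telephone screen: "they will come to the lab for an informed consent meeting".
- Section V.A gives the within-subject factor as "time of data collection (0, 1, 6, and 12 months").
- Section II.F.a.ii, on people taken off the study for a medical reason that the study doctors accept: they "will receive the same reimbursement as if they completed the study".

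**The concern.** A flat completion payment beside an uncapped per-visit payment can cross over. If enough visits are paid, someone who attends all but the last collects more than someone who attends them all. The last visits belong to the 12-month assessment, the time point on which section II.C bases the sample size. A payment rule that favoured skipping them would work against the data the trial most needs.

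The crossing seems within reach. The in-person screening steps described are a consent meeting, a blood draw and a stress test. If these take one to three of about 13 visits, 10 to 12 visits remain to be paid.

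In addition, III.G does not repeat the rule in II.F.a.ii for medical discontinuation. Read by itself, III.G would pay such a participant much less than II.F.a.ii promises.

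**Working it through.** **Inputs.** Completion payment 600 dollars and early-leaver rate 75 dollars per non-screening visit (III.G); about 13 visits in total (II.E). The number of paid visits, N, is not given, so it is varied.

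**1. The plan's own figure.** The protocol does not derive the 600. Dividing by the rate gives 600/75 = 8 exactly. The completion payment is therefore the full prorated sum if 8 visits are paid, for example two at each of the four time points in V.A.

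**2. Where the payments cross.** Leaving just before the last paid visit yields 75 × (N − 1). Setting this equal to 600 gives N = 9.

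| Paid visits N | 75 × (N − 1) | Against 600 |
|---|---|---|
| 8 | 525 | −75 |
| 9 | 600 | 0 |
| 10 | 675 | +75 |
| 11 | 750 | +150 |
| 12 | 825 | +225 |

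A reversal needs N of 10 or more.

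**3. What that needs from the visit total.** With T visits in all and s of them screening, assuming every other visit is paid, N = T − s. A reversal needs s ≤ T − 10. For T = 13 that is at most 3 screening visits. If the approximate total is taken as 12 or 14 (an assumed range), it is at most 2 or 4.

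**4. Splits that fit 13.** All three are assumptions:

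- 1 screening visit and 3 at each of four time points: 1 + 3 × 4 = 13, so 12 paid and a reversal.
- 2 screening visits, then 3, 2, 3 and 3 at months 0, 1, 6 and 12: 2 + 11 = 13, so 11 paid and a reversal.
- 5 visits before randomisation all treated as screening, then 2, 3 and 3 at months 1, 6 and 12: 5 + 8 = 13, so 8 paid and no reversal.

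The last two allow for a lighter month 1: the glucose tolerance test (II.E.a.iv) and the cardiovascular measures (II.E.a.xii) are repeated only at 6 and 12 months. The third is open because the line between screening and baseline is not sharp. II.F.a.i calls the maximal stress test a screening step. II.E.a.xi treats maximal exercise testing as an outcome repeated at 1, 6 and 12 months, which implies a baseline value.

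**5. Missing the whole 12-month assessment.** Skipping a block of b visits pays 75 × (N − b).

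| N | b = 2 | b = 3 | b = 4 |
|---|---|---|---|
| 12 | 750 | 675 | 600 |
| 11 | 675 | 600 | 525 |
| 10 | 600 | 525 | 450 |

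Even with 10 to 12 paid visits, this beats 600 in 3 of 9 cells, ties in 3 and falls short in 3. Any gain concerns mainly the single last visit. The order of visits at month 12 is not given, so that visit need not be the biopsy.

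**6. Medical discontinuation.** After 4 paid visits, III.G alone gives 4 × 75 = 300, where II.F.a.ii gives 600. The second is a specific rule for a defined group and the first a general one. Applied together, they pay 600.

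**The case for a change.** The best case for acting is that the screening steps actually described fill at most three visits. The reading with 8 paid visits needs about five unpaid ones, and no section lists five. Extra safety blood draws add a second route. If they are paid, then 8 scheduled visits plus two extra draws give (7 + 2) × 75 = 675 for leaving before the last visit, against a flat 600. A stated maximum would close both routes at almost no cost, and if 8 or 9 visits are paid and extra draws are not, a limit of 600 would alter no payment.

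Some of this stands. III.G is silent on the count and on a maximum, and the threshold of 10 is exact. What does not stand is the step from possible to likely. The count of three screening visits leaves out baseline testing, which precedes randomisation and may be handled as unpaid screening. The argument from extra draws assumes both that they are paid and that a participant has two of them. Against these assumptions is an even division, 600/75 = 8, in a plan described as prorated. The consent form is not among the documents reviewed and may list the paid visits, so silence in III.G does not show that participants are left uninformed.

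**Conclusion.** No change to the plan is called for. The wording is incomplete but no wrong sum is shown. The payments are consistent with 8 paid visits, tie at 9 and reverse only from 10, and the documents do not settle which applies. Over the range considered, the difference for missing only the last visit lies between −75 dollars (8 paid) and +225 dollars (12 paid) per participant.

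Nothing statistical depends on it. The rule is identical in the three arms, the sample-size calculation does not use it, and the mixed model described in II.C and V.A can include participants with missing visits. Any effect on retention would be inference. Study staff must fix the number of paid visits before they can pay anyone, and the medical-discontinuation rule in II.F.a.ii already covers the people it was written for. Stating the count and a ceiling of 600 dollars would be tidy if III.G were being edited for another reason.

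This conclusion rests on two assumptions: that the visits counted in II.E are the study visits meant in III.G, and that II.F.a.ii governs medical discontinuations.

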To examine the potential acute impact of statins on mitochondrial function in vitro, we obtained skeletal muscle biopsies from sedentary healthy humans (N=7, 25-50 years of age, 12h fasted, no history of elevated lipoproteins or statin use, normal liver function), and exposed permeabilized fiber bundles to vehicle (DMSO), simvastatin (2.5 μ M) or atorvastatin (10 μ M) for 10 min and throughout subsequent substrate additions (37°C). Maximal ADP-stimulated O₂ consumption rate (JO₂) during respiration supported by glutamate/malate (complex I substrate; Fig. 3A) or succinate (complex II substrate; Fig. 3B) plus rotenone (to block reverse electron flow) was ~30- 50% lower after acute exposure to either

statin compared with vehicle alone. These findings suggest that statins may directly interfere with mitochondrial respiratory function independent of their effect on mevalonate synthesis.

To examine the potential impact of statin therapy on skeletal muscle mitochondrial function in vivo, a preliminary repeated measures study was conducted on six sedentary participants (36.3 ± 3.4 y, 31.9 ± 0.7 BMI, VO₂peak=24.7 ± 1.9 ml/kg/min) with no history of elevated lipoproteins or statin use.

After baseline testing (Day 0), participants began statin therapy (80 mg/kg/day atorvastatin) and were retested after 14, 28 and 56 days. Total cholesterol (mean \pm SE) decreased from 182 \pm 27 to 123 \pm 16 mg/dl and LDL decreased from 120 \pm 26 to 64 \pm 15 mg/dl by day 56. Plasma creatine kinase, ALT and AST levels did not change indicating no skeletal muscle or liver damage. At the whole muscle level however, non-invasive determination of O₂ recovery kinetics in vivo by near infrared spectroscopy (NIRS) revealed a ~20% statin-induced decrease in maximal mitochondrial function (Fig. 4A). Specifically, note the decrease in the mVO₂ rate constant (Fig. 4A

[figure not shown]

Fig. 3. In vitro acute exposure to statins decreases mitochondrial respiratory capacity. See text for explanation.

inset), which is directly related to mitochondrial respiratory capacity (46). At the level of the mitochondria in muscle, maximal ADP-stimulated respiration progressively decreased over the duration of statin therapy to \sim 50% of pretreatment values (Fig. 4B). This striking decrease was also evident in three other titration protocols using different substrates (data not shown). Importantly, addition of

[figure not shown]

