- iv. Intravenous glucose tolerance test (IVGTT): The subject will arrive following an overnight fast (10-12 hrs). Upon arrival, anthropometrics and vital signs will be measured. A catheter will be placed in one arm for blood draws. A fasting blood draw (~14-16mls) will be used to determine blood glucose, insulin, total cholesterol, HDL-C, LDL-C, triglycerides. Creatine kinase (CK) and liver enzymes (ALT) will be tested at 6 and 12 months during IVGTT. CK and ALT will be used to detect abnormal myopathy, and changes in liver function from statin use for participant safety. Following the baseline draw glucose (50%) will be injected at a dose of 0.3 g/kg. First, 10 units of insulin will be pulled into an insulin syringe. Then 90 units of saline to fill the syringe. The mixture with be wasted down to the calculated dose (body mass in kg X 0.025). Then 4 ml of saline will be pulled into a 5ml syringe. The insulin/saline mixture will then be injected into the 5ml syringe. A dose of 0.025 U/kg body mass will be administered at minute 20. These mixing procedures have been safely preformed at the CTSU for a recent study (INFORM; HSC#13453). Serial blood samples (28 total) will be obtained from the other arm at minutes 2, 3, 4, 5, 6, 8, 10, 12, 14, 16, 19, 22, 23, 24, 25, 27, 30, 40, 50, 60, 70, 80, 90, 100, 120, 140, 160, and 180. Plasma will be frozen at -80°C for later determination of glucose and insulin, and insulin sensitivity will be calculated using a minimal model program (77). A total of approximately 622 ml of blood will be collect over the 12 month intervention. After analysis for current project is complete any remaining blood samples will be stored indefinitely for future research. Fasting blood draw will be repeated at 1, 6, and 12 months. The IVGTT will be repeated at 6 and 12 months.

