- xi. Exercise Testing: Whole body steady state submaximal O₂ consumption will be determined during a standard 6 min treadmill test (2.5mph) to determine VO₂ cost. Participants will then complete a ramped treadmill test (Bruce protocol) to determine cardiorespiratory fitness (VO₂ peak) and peak heart rate as previously described (13). We will also investigate post exercise oxygen consumption and heart rate at 60, 90, 120, and 300 seconds after cessation of the max test to determine if exercise recovery is impacted by statins. Blood will be sampled for measurement of CK 20-30 minutes following the maximal exercise to assess potential muscle damage. Exercise testing will be repeated at 1, 6, and 12 months.
- xii. Cardiovascular Function: These measures include both heart rate and stroke volume performed under both resting and sub-maximal exercise conditions (performed on separate days) (80). Stroke volume will be estimated by finometer placed on finger (80). Cardiovascular function will be repeated at 6 and 12 months.
- xiii. Physical Activity Monitoring: Physical activity levels and sedentary time will be assessed by pedometers and accelerometers for 5 day periods. Physical activity monitoring will be repeated at 1, 6 and 12 months.
- xiv. Statin Therapy Intervention: Once participants have successful completed baseline testing, the participant will be randomly assigned to 1 of 3 groups (1:1:1 ratio). Statins will be prescribed as a placebo or at a dosage of 20 or 80 mg/day (atorvastatin; Lipitor) by the study physician at KUMC, [name], MD. Participants and research team will be blinded to the type and dose of statin. Statins will be dispensed by KUMC investigational pharmacy at regular intervals during the participant's enrollment in the study. The study physician will provide care for any problems associated with the statin treatment after unblinding by Data Safety Monitoring Board, [name]. All doses fall within the norms of recent recommendations and are given chronically (2).

F. Risk/benefit assessment:

a. Potential risks:

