 - c. Providing on-going information to the study sponsor and the IRB: PI, Study Coordinator
 - d. Maintaining participant's research records: PI, Study Coordinator
 - e. Completing physical examination: PI, CTSU Nurse
 - f. Taking vital signs, height, weight: CTSU Nurses
 - g. Drawing / collecting laboratory specimens: CTSU Nurses
 - Performing / conducting tests, procedures, interventions, questionnaires: PI,
 Study Coordinator
 - i. Completing study data forms: Study Coordinator
 - j. Managing study database: PI

K. Assessment of Subject Safety and Development of a Data and Safety Monitoring Plan

- **a. Key personnel:** [name], [name], [name], [name], study physician at KUMC and [name], study physician at ECU.
- b. Plan for safety monitoring and review: [name] will serve as the Chair of the Data Safety Monitoring Board and will convene every 6 months with the other members, Drs. [name] and [name] to make decisions on safety of the participants. Enrollment data will also be reviewed twice a year by the DSMB. In addition, data will be reviewed on a yearly basis with the biostatistician, [name] to determine if the studies should be shortened do to either no measured effect or due to effects that are greater than what power calculations indicated. If problems occur with participants, blinded study staff will alert [name]. [name] will have access to dose and type of statin and will consult the study physicians/cardiologist to make a decision on whether the subject should be removed from the study for safety concerns. The PI and other key personnel will be examining research data on a subject to subject basis to ensure it is accurate and to address any potential problems that may arise with the protocols. In addition, Drs. [name] and [name] will discuss data at least once per month through in person meetings or by phone to ensure that data collection is occurring in a consistent manner at both locations.
- **c. Plan for adverse event reporting:** Adverse events will be defined as any untoward medical occurrence in study participants or others immediately involved in the

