injury. In spite of all safety measures, you might develop medical problems from participating in this study. You must report any suspected illness or injury to the study coordinator immediately. If such problems occur, you will be provided with emergency medical treatment and the investigator will assist you in getting proper follow-up medical treatment. Neither the investigator nor the sponsor will provide compensation for research-related injuries. Payment of lost wages, disability or discomfort is not available. You do not give up any of your rights by signing this form."

IV. Data Collection and Protection

- A. Data Management and Security: All identifiable files, data, and tissue will be coded and stored in secure locations. These data include: study progression, subject numbers, percent completion, data quality, subject retention, adverse events, etc. The PIs at both KUMC and ECU will be responsible for the quality of the data and will supervise the data acquisition with the help of study coordinators. All data will be coded for confidentiality, and only the PI, study coordinator, and study statistician will have access to the code. The results of each test on each subject will be screened by the study coordinator prior to entering on the spreadsheet. This is standard practice in our laboratories. Hard copies are kept in dedicated locked cabinets. Specific coded subject files will be sent to the study statistician for statistical analyses. These analyses will be sent to the PI and study coordinator for dissemination to appropriate co-Is. At the end of participation in the study, each subject will receive a personal data summary of their test results. The study coordinator or a study investigator will discuss the results with the subject. After 1 year, the PI's including the biostatistician, [name] will be un-blinded but the study staff will remain blinded, so that the important research findings can begin to be delineated. This will also allow for [name] to being to examine if the trial is finding more or less significant effects for outcome measures.
- **B. Sample / Specimen Collection:** All participants will be assigned a data code. Blood and tissue samples will be labeled with the participant's data code and stored in a locked freezer. Blood and tissue samples will be stored indefinitely following completion of current project for future research.

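### On-treatment lipid results are not withheld from staff who may run later tests, which puts assessor blinding at risk for staff-administered secondary outcomes

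*Combined protocol and SAP*

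**What the plan says.** The blinding commitment is in II.E.a.xiv: "Participants and research team will be blinded to the type and dose of statin". IV.A repeats it for staff: when the PIs and the biostatistician are unblinded after one year, the study staff are to stay blinded.

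The lipid measurements are in II.E.a.iv. The fasting sample "will be used to determine blood glucose, insulin, total cholesterol, HDL-C, LDL-C, triglycerides", and "Fasting blood draw will be repeated at 1, 6, and 12 months".

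Two routes bring individual results to the team. In IV.A: "The results of each test on each subject will be screened by the study coordinator prior to entering on the spreadsheet". In II.K.b, and again in IV.E: "The PI and other key personnel will be examining research data on a subject to subject basis to ensure it is accurate". Neither makes an exception for lipids.

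The same roles are listed for testing. The II.J entry reads "Performing / conducting tests, procedures, interventions, questionnaires: PI" and goes on to name the study coordinator. II.J also lists these two roles as present during study procedures.

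The size of the drug's effect on LDL is in the pilot results of I.C: "LDL decreased from 120 \pm 26 to 64 \pm 15 mg/dl by day 56".

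**The concern.** Atorvastatin moves LDL by an amount that a reader of individual results can recognise. A coordinator who screens a participant's month-1 panel as IV.A requires, and then helps run that participant's later tests, may have a good idea whether the participant is on statin or placebo. This needs no protocol deviation: it follows from the stated screening rule. Data codes do not prevent it, because IV.A gives the PI and coordinator access to the code.

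At stake are the secondary outcomes that staff administer: treadmill VO2peak (II.E.a.xi), isometric strength (II.E.a.viii), and pressure pain threshold and pain ratings (II.E.a.vii). Encouragement, instruction and the way a rating is asked for can shift these. The protocol states a directional hypothesis (I.A, V.B), so any such influence would probably favour the expected result.

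This is separate from the planned unblinding of the PIs. It can start with the month-1 panel, and it reaches staff who are meant to remain blinded throughout.

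**Working it through.** The plan gives no figure for how well allocation can be guessed, so there is none to reproduce. The sample size and alpha in II.C do not enter.

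**Inputs from the documents.** Pilot LDL 120 mg/dl at baseline and 64 mg/dl at day 56, with ± values 26 and 15 on six participants (I.C, which labels the lipid summary as mean ± SE). Allocation 1:1:1 (II.C).

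**Assumptions, because the documents give no values.** Placebo mean change 0%. SD of percent change 10, 15 or 20 points, equal in all arms. Mean fall on 20 mg between 25% and 40%. Normal distributions.

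**Step 1, pilot fall.** (120 − 64)/120 = 46.7%, taken as 47%.

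**Step 2, 80 mg against placebo.** With a cut at the midpoint, the proportion correctly classified is Φ((47/2)/SD) = Φ(23.5/SD).

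**Step 3, 80 mg against 20 mg.** For a mean 20 mg fall of m, the proportion is Φ(((47 − m)/2)/SD).

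**Step 4, exact arm among three.** With equal priors and cuts midway between adjacent means, the proportion is [2Φ((m/2)/SD) + 2Φ(((47 − m)/2)/SD) − 1]/3. For m = 25 and SD = 10: [2(0.894) + 2(0.864) − 1]/3 = 0.84.

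**Step 5, any statin against placebo.** Each value of LDL change is assigned to the likelier of placebo and the two statin arms combined, integrated numerically.

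Where two figures are given, the first is for m = 25 and the second for m = 40.

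| SD of % change | 80 mg v placebo (chance 50%) | 80 mg v 20 mg (chance 50%) | Exact arm (chance 33%) | Any statin v placebo (67% by always guessing statin) |
|---|---|---|---|---|
| 10 | 99% | 86%, 64% | 84%, 74% | 93%, 98% |
| 15 | 94% | 77%, 59% | 71%, 67% | 86%, 93% |
| 20 | 88% | 71%, 57% | 63%, 61% | 81%, 87% |

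If the mean fall on 80 mg were only 30% (assumed), Φ(15/SD) gives 93%, 84% and 77% against placebo.

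**Step 6, absolute change using the pilot's own spread.** Reading ± as SE with n = 6, the SDs are 26√6 = 63.7 and 15√6 = 36.7 mg/dl. The SD of change is √(63.7² + 36.7² − 2r × 63.7 × 36.7). With r from 0.3 to 0.9 (assumed) it runs from 63.3 down to 34.6 mg/dl. With a cut at 56/2 = 28 mg/dl and the same SD assumed on placebo, accuracy is Φ(28/63.3) = 67% to Φ(28/34.6) = 79%. If the ± values were SDs instead, it would be 86% to 98%.

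**Step 7, timing.** No section says when lipid results return. Three places suggest that it is before month 6. II.A.b.iv lists lipids in the same fasting samples as CK and ALT, and the month-1 CK and ALT results are used for withdrawal decisions (II.D.b). II.E.a.iv describes freezing for later assay only for glucose and insulin. V.B says that most data are analysed as the study goes on. Return before month 6 is likely, but it is an inference.

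**The case against.** The case against has force on several points.

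- **Participants stay blinded by this route.** They receive their lipid profile only at the end of participation (V.C), and III.F releases nothing else except new risk information. They supply the effort and give the pain scores. A reader might infer that the double-blind comparison is lost; the documents support only a risk to assessor blinding.
- **The 20 mg arm matters.** High against low dose is one of the two primary comparisons in II.C, and there a single LDL change may do little better than chance. A reader might infer that the month-1 panel reveals most allocations. The documents do not establish that, since they give neither a 20 mg LDL effect nor an SD of percent change.
- **The pilot figure is weak.** It is a day-56 value, not month 1. I.C reports six participants where II.C reports eight, and I.C prints the pilot dose per kilogram where the rest of the protocol uses mg per day; these passages must be reconciled.
- **II.J is a generic role list.** II.E.a.viii assigns strength testing to trained staff, and II.F.a.i mentions a medical monitor for the graded exercise test. No section says who runs each visit or who performs respirometry.
- **The primary outcome is different in kind.** It is duplicate laboratory respirometry (II.A.a.i). A reader might suspect influence on repeat biopsies or assays, but a second pass depends on low tissue yield and the participant's consent (II.E.a.v), and no repeat-assay rule is given.

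All of this narrows the point. It does not supply the missing provision: no section withholds on-treatment lipids from people who may conduct later tests, and no separate blinded assessor is named.

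**Conclusion.** The gap is real and worth closing. The stated screening and review rules give individual on-treatment LDL to roles that are also listed as conducting tests, against the protocol's own commitment to blinded staff. The consequence is a risk to assessor blinding for staff-administered secondary outcomes, mainly in comparisons of statin with placebo.

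The 88% to 99% range for 80 mg against placebo rests on the pilot mean and an assumed SD. The 67% to 79% range uses the pilot's spread with an assumed correlation. Both are above the 50% expected by chance, but the distance between them shows how little the documents fix the size. For 80 mg against 20 mg (57% to 86%) and for the exact arm (61% to 84%), the 20 mg effect is assumed as well.

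Confidence is medium: the access to results and the absence of masking are in the text, while the timing of results and who runs each test are inferred. The point changes neither the sample size nor the error rate.

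**What to change.** Amend IV.A and II.E.a.iv as follows, and align II.K.b and IV.E:

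- Exclude post-randomisation total cholesterol, LDL-C, HDL-C and triglycerides from the coordinator's result screening and from the subject-by-subject review by the PI and key personnel.
- Have the laboratory send them to the role that II.K.b already designates to hold allocation and to the DSMB, and transfer them directly to the database or the statistician.
- Withhold them from anyone who conducts or scores that participant's tests until the month-12 tests and assays are complete.
- State that CK, ALT and creatinine reporting, and the study physician's access to safety laboratory results, are unchanged.

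The cost is protocol wording and a different laboratory report route. It needs no added visits, tests, participants or staff. The downside is that lipid data queries fall to the unblinded role. For the PIs themselves, masking lipids gains little once the unblinding planned in IV.A takes place; the benefit is for the coordinator and testing staff.
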